6.11. Study duration

Recruitment and data collection is expected to begin upon approval from the IRB and FDA and continue for seven months. We estimate a total of four months for final data analysis. Total estimated study duration is eleven months (Table 6).

6.11.1. Subject participation duration

Including the screening visit, a two to four-week interval between doses, and an exit phone interview for adverse event monitoring, it will take a participant six to eight weeks to complete the study.

Table 6. Study timeline.

Activity	Month	1-3	4-6	7-9	10-12
Finalize product manufacture/quality control					
Recruitment/enrollment					
Data collection					
Data analysis/summary					
Reports, manuscripts					

7. PROVISIONS TO MONITOR THE DATA TO ENSURE SUBJECT SAFETY

Adverse event (AE) monitoring will occur in “real time” using a standardized Adverse Event Monitoring Form and reviewed weekly by the principal ([name]) and clinical ([name]) investigators. This form is a ninety-one point multi-system questionnaire that assesses all organ systems (eyes/ears/nose/throat, gastrointestinal, neurological/ musculoskeletal, psychological/general, cardiopulmonary, skin, genitourinary and whole body systems). It will be completed at the screening visit in order to collect data on any/all pre-existing symptoms and their severity, and will serve as baseline data to determine attribution to the study intervention. The Adverse Event Monitoring Form will be administered in person at the beginning and end of Visits 1 and 2, via telephone the day following Visit 1 and 2, and by telephone one week after Visit 2, to assess for acute and delayed adverse events. Electrocardiograms will be performed just prior to administration of *Centella asiatica* product and six hours after intervention to monitor for adverse events. This time point has been selected based on prior pharmacokinetic literature on *Centella asiatica* triterpenes and from our murine studies which suggest that at 6 hours, the bioactive triterpenes should have reached maximum concentration and the caffeoylquinic acids are beyond their time of maximum concentration. This is also to allow for the collection of the ECG to be feasible given the frequent timing and short intervals between blood sample collection earlier in the experiment. A comprehensive metabolic panel (CMP) will be measured at baseline of each study visit and at 10 hours after CAP administration to assess for liver or kidney toxicity. This time point was selected to allow for markers of toxicity to develop if present, and for logistical reasons to allow adequate time for sample collection, processing and transfer to the OHSU Core Laboratory for analysis within the 10 hour time frame of the experiment.

Participants will be reminded and encouraged during clinic visits to contact a study clinician if a moderate or serious AE occurs. Participants will be given a telephone number they can call at any time to report potential adverse effects. All severe AEs will immediately be reported to the Independent Monitoring Committee (IMC) and the OHSU IRB by the study principal investigator.

An **adverse event (AE)** is defined as any unfavorable and unintended diagnosis, symptom, sign (including an abnormal laboratory finding), syndrome or disease which either occurs during the study, having been absent at baseline, or if present at baseline, appears to worsen. Adverse events are to be recording regardless of their relationship to the study intervention.

A **serious adverse event (SAE)** is defined as any untoward medical occurrence that results in death, is life threatening, requires inpatient hospitalization or prolongation of existing hospitalization, results in persistent or significant disability/incapacity, or is a congenital anomaly.

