1.4. Specific aims

Aim 1: To assess the bioavailability and rate of clearance of *Centella asiatica* derived compounds in mildly demented elders on cholinesterase inhibitor therapy through a pharmacokinetic study.

- **Hypothesis:** We hypothesize that the triterpene and caffeoylquinic acid components from *Centella asiatica* will be bioavailable, and a dose giving similar plasma levels to those associated with cognitive effects in mice can be achieved.

Aim 2: To determine the acute tolerability of a *Centella asiatica* product in mildly demented elders on cholinesterase inhibitor therapy.

- **Hypothesis:** We hypothesize that acute usage of the *Centella asiatica* product will be well tolerated and produce no severe adverse events.

Aim 3: To investigate whether activation of the NRF2 antioxidant pathway can be detected in PBMC of mildly demented elders on cholinesterase inhibitor therapy following ingestion of a *Centella asiatica* product.

- **Hypothesis:** We hypothesize that activation of the NRF2 pathway can be measured as increased NRF2 gene expression and/or nuclear protein levels in PBMC during a 6 hour period following ingestion of the *Centella asiatica* product.

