5.9. Criteria for intervention discontinuation and stopping guidelines

Participants will be advised during the informed consent process that they have the right to permanently discontinue the *Centella asiatica* product and/or withdraw from the study at any time without negative repercussions. Participants will also be counseled during the consent process that they may be withdrawn from the study at the discretion of the Principal Investigator or designees. A participant may discontinue and/or withdraw and/or be withdrawn from the study for the following reasons:

Administrative:

- 1) Withdrawal of participant consent
- 2) Request of site investigator or designees
- 3) Request of primary care physician
- 4) Non-compliance
- 5) Protocol deviation
- 6) Premature termination of the study

Adverse event (AE)/experience:

- 1) Worsening of pre-existing disease
- 2) Intercurrent illness
- 3) Death
- 4) Major/clinically significant alteration in laboratory values or biometric assessments after beginning product
- 5) Other AE
- 6) Other reasons concerning the participant's health or well-being

The study will be terminated if two participants terminate due to intervention-related adverse events. Severe adverse events will be reviewed immediately by the Principal Investigator, clinical investigators and the Independent Monitoring Committee (IMC) to determine if severity and relatedness warrant termination of the study.

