7.2. Independent Monitoring Committee (IMC)

Data monitoring and safety oversight is to be carried out via an independent monitoring committee (IMC) composed of at least three members beyond the principal study team. A clinician with experience in relevant disease research will chair the IMC and the other two members will be a statistician and a second clinician with human subject research monitoring expertise. An IMC is planned over a Data Safety Monitoring Board (DSMB) based on the National Institute of Health (NIH) and National Center for Complementary and Integrative Health (NCCIH) listed criteria with respect to data safety and monitoring. This study is single-site and phase I trial in scope. In addition, *Centella asiatica* is expected to be largely safe based on pre-clinical work and its long-standing position and extensive usage in herbal medicine. However, the use of blinded randomization and an elderly study cohort predicates the use of a multi-person committee and not just an independent monitor. See IMC charter.

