7.3. Plan for review and reporting

The IMC will meet biannually to study un-blinded AE data coded by organ system, and on an ad-hoc basis as necessary, based on the cited reporting of severe AEs and continuing reviews to OHSU's IRB. Should it be determined that the protocol need to be amended as a result of data review, the principal investigator will submit a protocol amendment to the sponsor (NCCIH) for approval. Once approval is obtained from the sponsor, the amendment will be submitted to the OHSU IRB and monitoring body and the amendment approved prior to study amendment implementation, unless immediate implementation is required to protect the safety of the study participants. In such a case, the protocol amendment will be immediately implemented and the sponsor, OHSU IRB and IMC will be notified directly after protocol amendment implementation.

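### The expedited safety rules are triggered by 'severe' adverse events, so read literally they miss a serious adverse event of lesser intensity

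*Combined protocol and SAP*

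**What the plan says.** Three rules call for prompt independent attention, and all three use the word 'severe':

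- Section 7, reporting: "All severe AEs will immediately be reported to the Independent Monitoring Committee (IMC) and the OHSU IRB by the study principal investigator".
- Section 5.9, termination: "Severe adverse events will be reviewed immediately by the Principal Investigator", together with the clinical investigators and the IMC, to decide whether the trial should stop.
- Section 7.3, meetings: the IMC meets twice a year on un-blinded adverse event data and "on an ad-hoc basis as necessary, based on the cited reporting of severe AEs and continuing reviews to" the IRB.

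The word also appears in the Aim 2 hypothesis (section 1.4), that acute use of the product "will be well tolerated and produce no severe adverse events". No action follows from it there.

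The term that section 7 defines is a different one. A serious adverse event "is defined as any untoward medical occurrence that results in death, is life threatening, requires inpatient hospitalization" or its prolongation, or leads to lasting or significant disability, or is a congenital anomaly. The only other use of 'serious' for handling events in this trial is the instruction that participants be "encouraged during clinic visits to contact a study clinician if a moderate or serious AE occurs".

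Section 7.2 describes the committee and ends with "See IMC charter". The charter is not among the supplied documents.

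**The concern.** Severity describes how intense an event is. Seriousness describes what it led to. The two overlap but are not the same: a short admission for observation is serious by the section 7 definition even if the event was moderate in intensity. Here the defined category starts no expedited step, and the category that starts all of them is not defined in the supplied text.

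What is at stake is the timing of independent review. Each participant takes a second dose, possibly the higher one, two to four weeks after the first. Section 2.5.4 says there are no human safety data for concentrated water extracts at these doses, and section 7.2 gives the elderly cohort as one reason for a multi-person committee. If a participant were admitted to hospital after Visit 1, one would expect the IMC to hear of it before that participant is dosed again. The rules as worded do not require this unless the event is also called severe.

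**Working it through.** No arithmetic decides this point. The check is to set each use of the two words beside the action attached to it.

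| Section | Word applied to adverse events or effects | IMC or IRB action attached |
|---|---|---|
| 1.4 (Aim 2) | severe | none (hypothesis) |
| 5.9 | severe | immediate review for termination, including the IMC |
| 7 | severe | immediate report to IMC and IRB |
| 7.3 | severe | ad hoc IMC meeting |
| 2.5.4 | serious | none (literature summary) |
| 7 (participant instruction) | serious | none (participant contacts a clinician) |
| 7 (definition) | serious | none |

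'Severe' is used 4 times, 3 of them with an IMC or IRB action. 'Serious' is used 3 times, none with such an action. The abbreviation SAE occurs only in its own definition.

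**Can 'severe' fairly be read as intensity?** Yes. Section 7 says the adverse event form records pre-existing symptoms and how severe they are. Section 7.1 decides attribution by comparing greater and lesser severity with baseline. Section 5.9 treats severity and relatedness as the two things to weigh for termination. In each place severity means degree.

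**Which serious events would escape?** The definition has 5 criteria. Death and life-threatening events are severe on any ordinary reading. Significant disability usually would be. A congenital anomaly is close to moot at age 65-85. Hospital admission, or its prolongation, is the criterion that can plausibly be met at less than severe intensity.

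**What happens to such an event, read literally?** It is still an adverse event, so these routes to the IMC remain:

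- The twice-yearly un-blinded review (section 7.3). If the meetings are about six months apart, which is an assumption, the wait could exceed both the 2-4 weeks to the second dose (section 6.9) and the six to eight weeks a participant spends on study (section 6.11.1).
- Ad hoc meetings as necessary, based also on continuing reviews to the IRB (section 7.3). These are discretionary.
- Modification of the intervention on the IMC's recommendation when adverse events are noted (section 5.8). This sets no time for the IMC to be told.
- The rule that stops the study once two participants terminate for intervention-related events (section 5.9). One event does not meet it, and relatedness is judged by a study clinician with the principal investigator (section 7.1).

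None of these guarantees that a single serious event is reviewed independently before that participant's second dose.

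**Exposure.** 8 participants × 2 doses = at most 16 single doses. An event after the first dose can precede at most 8 × 1 = 8 second doses. The documents give no basis for estimating how often a hospital admission would occur.

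**The case against.** The strongest reply is that the authors used the two words as synonyms. The participant instruction pairs 'moderate' with 'serious', as if 'serious' were a step on an intensity scale, and the SAE definition follows shortly after the reporting rule in the same section. On that reading an admission triggers all three rules and only the terminology is at fault. This is probably what was meant. It supports correcting the wording, because staff must apply the rule as printed and sections 7 and 7.1 elsewhere use severity for intensity.

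A reader might infer that serious events fall outside IMC oversight altogether. The documents do not support that: sections 5.8, 5.9 and 7.3 give the IMC routes that do not depend on the word 'severe'. What is missing is an expedited or SAE-specific step.

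A reader might also infer that a participant could be dosed again with nobody noticing the event. That is unlikely. The investigators review adverse events weekly (section 7), participants are telephoned the next day (section 6.10) and again three days before Visit 2 to confirm consent (section 6.5), the adverse event questionnaire is given at the start of Visit 2 (section 6.9), and section 5.9 lists several health-related grounds for withdrawal. These checks stand as real protection, but all are on the investigators' side and none requires prompt independent review.

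Finally, a reader might infer that the trial has no definition of 'severe'. That cannot be concluded. The charter was not supplied. Nor was the adverse event form, which by section 7 records severity. Either may define the term or state the SAE rule.

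**Conclusion.** The mismatch is real and lies in operative text. Three expedited rules depend on an intensity word that the supplied text does not define, while the defined outcome-based category triggers no expedited step. Read literally, an SAE of less than severe intensity, mainly a hospital admission, need not reach the IMC or IRB at once, and the IMC might first see it after the second dose.

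This is a minor correction. It concerns one SAE criterion in a trial of 8 participants, leaves endpoints and analysis untouched, and sits alongside several investigator checks. The conclusion rests on reading 'severe' as intensity and on the charter and adverse event form not already settling the matter. If the authors meant 'serious', the change only makes the text say so.

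**What to change.** In sections 5.9, 7 and 7.3, replace 'severe' with 'serious (as defined in section 7, regardless of intensity) or severe'. Keeping both words brings in every SAE without dropping events that are severe but not serious. If the IMC charter already requires immediate reporting of SAEs, a cross-reference to it in section 7 would also serve, provided sections 5.9 and 7.3 are aligned with it.

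The cost is a wording change in three places and possibly a few more expedited reports. Endpoints, analysis, sample size and visits do not change.

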7.1. Attribution to intervention

At each administration, items identified on the Adverse Event Monitoring Form will be compared to baseline levels to determine if the symptom was pre-existing. If the symptom was pre-existing at the same or a previously greater severity, the symptom will *not* be considered attributable to the study intervention. If the symptom was pre-existing at lesser severity (or was not previously present), the symptom may be considered attributable to the study intervention. If the intervention is considered attributable, a study clinician, in consultation with the Principal Investigator, will determine if an alternative clinical explanation exists for the adverse event. If an alternative explanation does not exist, the adverse event *will* be considered attributable to the study intervention. If an alternative explanation does exist, the adverse event will *not* be considered attributable to the study intervention.

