5.10. Concomitant interventions

5.10.1. Allowed interventions: diphenhydramine, temporary use of sedatives for sleep (such as Ambien), probiotic supplements, non-plant based laxatives such as magnesium citrate or milk of magnesia, gastroesophageal reflux disorder medications such as antacids (non-flavored), central nervous system active medications that have been stable for greater than two months, analgesics

5.10.2. Required interventions: cholinesterase inhibitors therapy for the treatment of cognitive decline. The dose needs to be stable for a minimum of 12 weeks prior to study enrollment.

5.10.3. Prohibited interventions: sedatives (except those used occasionally for sleep), central nervous system active medications that have not been stable for two months (including beta blockers, cimetidine, SSRIs, SNRIs), anticoagulants (i.e. Warfarin), investigational drugs used within five half-lives of baseline visit, systemic corticosteroids, neuroleptics, anti-Parkinsonian agents, narcotic analgesics, nicotine (tobacco, patches, gum, lozenges, etc.), *Cannabis sativa* (herb or edibles), any over the counter or prescribed products containing plant extracts such as herbal supplements, plant based over the counter vitamin supplements, plant based over the counter protein powder supplements

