6.2. Recruitment

Participants will be enrolled on a rolling basis until the desired number of participants is achieved. Potential participants available through the above sources will be mailed a study advertisement describing the study and requesting they call if they are interested in participation. The study will be advertised using fliers in out-patient OHSU clinics, other regional hospitals within traveling distance to OHSU, local retirement communities/elder care facilities and an online posting in the March Wellness "March Stride" e-mail newsletter. In addition, it will be advertised using the NIH Clinical Trials website, local newspapers and radio announcements. We will also advertise through online social media platforms, such as targeted Facebook ads. We may also recruit by obtaining physician referrals from providers outside of OHSU using IRB approved recruitment materials. It will be emphasized that participation in the study is completely voluntary. Copies of all advertisements and non-OHSU physician referral request letters will be submitted for IRB approval.

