Sample collection: Participants will be asked to fast for 10 hours prior to each study visit, excluding water, in an attempt to standardize gastrointestinal transit time and minimize delayed absorption of the study intervention due to the presence of food. A study clinician or CTRC nursing staff member will place a peripheral intravenous catheter in the participant's arm or hand to allow for serial plasma specimen collection. Prior to administration of the *Centella asiatica* product, a baseline blood sample of one tablespoon (15 mL) will be collected through the catheter using a syringe and transferred immediately into a heparinized Vacutainer tube. The participant will be asked to consume by mouth one of the two doses of *Centella asiatica* product dissolved in 8-12 ounces of warm water, on an empty stomach in the presence of study personnel to ensure compliance. Participants will be asked not to consume food for two hours following consumption of the study intervention to allow for transition into the small intestine and absorption. If signs of hypoglycemia present, participants will be allowed to consume a high glycemic food and monitored for improvement. Serial blood samples (two or three teaspoons (10 -15 mL)/sample) will be obtained through the peripheral intravenous catheter using a syringe over a 10-hour post-administration period (15, 30, 45, 60, 90, 120, 150, 180, 240, 360, 480, and 600min) (Table 4). The 15 mL samples will be collected at 60, 120, 180, 240 and 360 mins to allow for 5 mL to be processed for PBMC isolation. Participants will collect their urine for the duration of the study visit (10 hours) to assess for excretion of *Centella asiatica* metabolites.

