8. RISKS AND BENEFITS

8.1. Risks to subjects

Potential harm to participants will be minimized by excluding participants with the conditions detailed in section 4.3.2. The risks to the subjects participating in this proposed research project are mainly those associated with venous access, potential toxicity of the test material, and time commitment.

Venipuncture: The potential risks to participants are minimal and reversible. Likely risks include pain and bruising from the intravenous catheter or venipuncture needle insertion. Occasional risks include feeling lightheaded or faint during or immediately after a blood sample is collected. Unlikely risks include swelling, infection, transient hematomas, transient thrombophlebitis, a fractured catheter embolus, or an allergic reaction to the adhesives or sterilization materials used at the venous access point. To minimize risk, catheter insertions and blood draws will be conducted in a seated position and using aseptic technique by trained personnel.

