Centella asiatica product: *Centella asiatica* is an edible plant. The Botanical Safety Handbook⁷⁸ classifies *Centella asiatica* as a Class 1 herb, i.e. one that can safely be consumed when used appropriately. The widespread use of *Centella* as a dietary supplement and human studies performed with *Centella asiatica*^{33-35,80,98,12} support its safety. At the doses given in this study, the risks are expected to be minimal and unlikely. The lowest dosage is based upon allometric scaling from mouse studies in which no toxicity was observed; however, the present product is a concentrated extract, and it is important to establish its safety, particularly in a vulnerable elderly population. We do not anticipate a great increase in adverse effects with the higher dosage, but are aware that they may occur. In particular, we anticipate potential transient gastrointestinal side effects such as nausea, gastric reflux/discomfort or diarrhea. Due to unknown interactions with pharmaceutical medications, we will exclude those on blood thinning medications (e.g. warfarin). We will also exclude those with hepatitis and/or liver disease, as there is potential for *C. asiatica* to harm the liver, and will closely monitor those on drugs with hepatotoxic potential (e.g., acetaminophen, methotrexate, pravastatin). *Centella asiatica* may cause sleepiness and drowsiness in large amounts, so individuals taking sedatives (besides occasionally for sleep) and Central Nervous System (CNS) depressants are likewise excluded, as the study drug could increase these side effects. Additional risks include allergic reaction to the intervention, which will be managed by oral or intravenous diphenhydramine depending on the severity.

Treatment-emergent suicidal ideation and behavior have been identified as a concern for a number of drugs and drug classes. Because of these concerns, a prospective assessment for suicidal ideation and behavior will be monitored. Heisel et al. (2011)¹³² have identified a “suicide ideation” subscale in the Geriatric Depression Scale (GDS). We are using the GDS as part of study procedures, and will pay special attention to the identified subscale questions to assess potential risk of suicidal ideation or behaviors.

Risks associated with a breach of confidentiality: There is a small risk that information about a study participant could be inadvertently disclosed to non-study personnel. Procedures to minimize this risk have been described in this protocol.

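### Section 7.1 drops attribution once an alternative explanation exists and has no contributory category, so a non-severe event that CAP helped cause can go uncounted in the two-termination stopping guideline (5.9)

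*Combined protocol and SAP*

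**What the plan says.** Section 7.1 (Attribution to intervention) works in two steps. A symptom already present at baseline at the same or greater severity is set aside. For a new or worsened symptom, a study clinician consults the Principal Investigator on whether there is an alternative clinical explanation. Two outcomes follow:

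- "If an alternative explanation does not exist, the adverse event" is attributed to the intervention.
- "If an alternative explanation does exist, the adverse event will" not be attributed.

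Section 5.9 contains the only numeric stopping guideline in the supplied text: "The study will be terminated if two participants terminate due to intervention-related adverse events". It does not define intervention-related and does not cite 7.1. Its next sentence sends severe adverse events to the Principal Investigator, the clinical investigators and the Independent Monitoring Committee (IMC), who judge severity and relatedness.

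Other safeguards do not depend on 7.1. Section 7 records adverse events whatever their relationship to the intervention and has the investigators review them weekly. Section 7.3 gives the IMC un-blinded adverse event data. Section 10.6 compares adverse event incidence between doses with no relatedness filter.

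**The concern.** The test in 7.1 is whether an alternative exists. It does not ask how likely that alternative is compared with CAP, or whether both contributed. Two joint-cause situations can be built from the protocol's own text.

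- **Lightheadedness.** Section 8.1 says of venipuncture: "Occasional risks include feeling lightheaded or faint during or immediately after a blood sample is collected". Section 6.9 schedules 13 samples per visit, so every participant has this alternative available. Section 2.5.1 also reports lower blood pressure in two six-month Centella studies, so a contribution from CAP is conceivable.
- **Drowsiness.** Section 8.1 says Centella in large amounts may cause drowsiness. It excludes regular sedative and CNS-depressant users "as the study drug could increase these side effects". Section 5.10.1 still allows temporary sleep sedatives and diphenhydramine.

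Read literally, either event is not attributable. If it ended participation, it would not count toward the two terminations in 5.9.

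The threshold is two among eight participants, so a single classification can decide whether the study stops. A missed count leaves others exposed. Recruitment is staggered ("Participants will be enrolled on a rolling basis until the desired number of participants is achieved"), each participant is due a second dose, and section 2.5.4 says there are no human safety data on concentrated water extracts at 2 g and 4 g.

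**Working it through.** The plan gives no operating characteristic for the stopping guideline, so there is no figure to reproduce. The documents also give no termination or misattribution rates. **Every rate below is assumed.** The calculation shows only what the rule can do.

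**Inputs from the documents**
- Participants: n = 8 (section 4.3.1).
- Trigger: 2 or more counted terminations (section 5.9).
- Anticipated dropout: 1 participant (section 4.3.1), or 1/8 = 12.5%. This is dropout for any reason, so using it for adverse event terminations is generous.

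**Model**

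X ~ Binomial(8, p), with participants independent, and P(X ≥ 2) = 1 − (1−p)^8 − 8p(1−p)^7.

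The counted rate is p = c(1−q) + u·s, where
- c = rate of CAP-caused terminations per participant,
- u = rate of unrelated terminations per participant,
- q = share of caused terminations lost to an alternative explanation,
- s = share of unrelated terminations counted because no alternative was found.

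**Step 1: under-counting alone (u = 0, q = 0.5)**

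| Assumed c | None lost | Half lost |
|---|---|---|
| 10% | 18.7% | 5.7% |
| 20% | 49.7% | 18.7% |

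This is one side of the rule only.

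**Step 2: both errors together**

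Split 12.5% equally, so c = u = 6.25%. The chance of two or more truly caused terminations is P(X ≥ 2; p = 0.0625) = 8.5%. The chance that the guideline triggers under 7.1 is:

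| q | s = 0 | s = 0.5 | s = 1 |
|---|---|---|---|
| 0.50 | 2.4% (p = 0.03125) | 8.5% (p = 0.0625) | 16.9% (p = 0.09375) |
| 0.25 | 5.1% (p = 0.04688) | 12.5% (p = 0.07813) | 21.5% (p = 0.10938) |

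The results lie on both sides of 8.5%. The rule under-counts on net only when c·q exceeds u·s, and the documents fix none of these four quantities.

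**Step 3: price of a graded rule**

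Suppose CAP causes no terminations (c = 0), unrelated terminations that would be graded possibly related occur at rate u, and half of them are already counted today.

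| Assumed u | All counted | Half counted (u/2) | Added chance of stopping |
|---|---|---|---|
| 2% | 1.03% | 0.27% | 0.76 points |
| 5% | 5.72% | 1.58% | 4.14 points |
| 12.5% | 26.4% | 8.5% | 17.9 points |

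The last row is an extreme case, in which the whole anticipated dropout consists of such events.

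**The case against.** **The test may be read more sensibly.** Whether an alternative explanation exists is a clinical judgement and can mean one that actually accounts for the event. That is fair. A reader might infer that 7.1 tells clinicians to accept even a far-fetched alternative. The text does not say so; it is silent on likelihood. Silence on contributory causes remains a gap in a rule that allows only yes or no.

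**Some examples are weak.** A reader might infer that the required cholinesterase inhibitor and the pre-visit fast give every participant a ready alternative. The inhibitor dose must have been stable for at least 12 weeks, the 10-hour fast comes before the visit, and the adverse event questionnaire is repeated at the start of each visit. Their effects should mostly show at the same-day baseline and would not readily explain a new symptom. The sedative statement in 8.1 is a reason for exclusion, so only occasional sedative or diphenhydramine use remains. Serial blood draws are the better example.

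**The guideline counts terminations, not events.** Transient lightheadedness or drowsiness may seldom end participation, and after Visit 2 only two phone calls remain. This narrows the concern but does not remove it.

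**The link to 5.9 is inferred, and other routes exist.** Section 5.9 does not cite 7.1, the IMC charter is not supplied, severe events have their own relatedness review, and 5.8 lets the IMC recommend changes after adverse events. All of this stands. What remains is the non-severe event that leads to termination. For that event, the scheduled IMC review is only biannual, against an expected seven months of recruitment and data collection (6.11).

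**A graded rule may overshoot.** In the middle case of Step 2 (q = s = 0.5) the current rule triggers 8.5% of the time, the same as the true chance. Recovering all caused events would raise this to 16.9% (s = 0.5) or 26.4% (s = 1). The arithmetic is right, but the match is two errors cancelling under chosen inputs. It is still a good reason to keep the revised threshold modest.

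**Conclusion.** The point holds as a limited defect in safety wording, of minor severity. Section 7.1 makes a new or worsened event not attributable once an alternative clinical explanation exists, without weighing it against CAP or allowing for a contributory cause. If 7.1 governs the undefined term in 5.9, a non-severe event to which CAP contributed can be left out of the two-termination count.

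Two stronger readings are tempting, and the documents support neither. One is that the guideline is biased toward letting the study continue. The rule also counts unexplained coincidental events, and under the assumed rates the trigger chance runs from 2.4% to 21.5% against a true 8.5%, so the net direction is unknown. The other is that safety data are lost. Recording, the comparison between doses and IMC review do not depend on attribution, and no endpoint, estimate or test changes.

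The conclusion rests on a literal reading of 7.1 and on the inferred link to 5.9. It does not rest on the assumed rates, which only illustrate that the error can go either way.

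**What to change.** In 7.1, keep the baseline comparison and, for symptoms that pass it, replace the last sentence with:

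> An event will be considered not attributable only if an alternative explanation is judged more likely than CAP and CAP is not judged to have contributed; otherwise it will be recorded as at least possibly related.

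In 5.9, add:

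> Intervention-related means at least possibly related under 7.1.

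Leave all-causality recording, the comparison in 10.6 and IMC review unchanged. Requiring the alternative to be *clearly* more likely is not needed and would push further toward over-counting.

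The cost is two or three sentences, one case report form field, and a somewhat higher chance of a precautionary stop. From Step 3, that is about 1 to 4 percentage points if unrelated terminations graded possible occur in an assumed 2% to 5% of participants and half are already counted. It reaches about 18 points only in the extreme 12.5% case. For a single-dose pilot in which direct benefit to participants is unlikely (8.2), that is a reasonable price. If the IMC charter already defines relatedness for the guideline, a cross-reference in 5.9 would be enough for that term.
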